## 6.4 Safety Analysis

### 6.4.1 Primary Safety Variable

Major bleeding as a primary safety outcome will be tested for a superiority by a log-rank test with a one-sided significance level of 0.025 using the AT population. Time from the study drug initiation date to the date of first adjudicated major bleeding or censoring will be determined as specified in Section 6.1.6.

A linearized event rate per arm is calculated as the total number of patients with adjudicated major bleeding divided by the total patient time (years) using the AT population. The major bleeding rate for both warfarin and apixaban arms will be compared with two times the major hemorrhage OPC, or 0.032/pt-yr (=3.2%/pt-yr). (Wu et al., 2014)

### 6.4.2 Secondary Safety Variables

All secondary bleeding definitions and clinical events cases defined in Section 7 of the study protocol will be summarized with frequencies and percentages per treatment group using the AT population.

## 6.5 Exploratory Analysis

The total DASS score as well as the 3 subscales (hassle, limitations, and positive impact will be analyzed as described below.

The EQ-5D-5L index, the subscales (mobility, self-care, usual activities, pain/discomfort, and anxiety/depression) as well as the EQ VAS score will be analyzed as described below. A repeated-measures mixed-effects model with Baseline score as a covariate will be run for each measure described above. The follow-up time-points responses (Month1, Month6, Month 12, and Month 24) will be included as outcome variables, and time as a fixed-effect variable.

Restricted maximum likelihood estimation will be used to model all available data from each subject without imputing missing values. An unstructured covariance matrix will be used, if the model doesn't converge, then a compound symmetry will be used.

Point estimates for each treatment group and treatment group mean differences (Apixaban - warfarin treatment) with 95% confidence intervals (CIs) will be generated for each time point. Additionally, the treatment effect will be averaged across all follow-up time points. The estimated treatment difference and 95% CIs will be obtained using the ESTIMATE Statement in SAS PROC MIXED. However, if the total missing value is greater than 10%, then descriptive statistics will be presented for the non-missing values by visits and overall.

“Total Missing” is derived as follows:

- Numerator: Number of participants missing measure of interest across visits
- Denominator: Number of participants expected to have the measure of interest across visits (# patients in population \* 5 visits). Denominator will not take into account when patients died, were lost to follow-up, or withdrew consent.

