#### 3.4 Quality of Life (EQ-5D-5L) Questionnaire

The survey is collected at Baseline, Month 1, Month 6, Month 12, and Month 24.

EQ-5D-5L questionnaire asks questions that are used to derive 5 subscales: mobility, self-care, usual activities, pain/discomfort, and anxiety/depression. Each question has 5 choices for health state ranging from best ("no problems") to worst. A Each subscale is created by summing up the answers to the questions affiliated with the subscale, ensuring that 1 is assigned to the answer indicating no problems and 5 is assigned to the answer indicating worst problem.

An index-based summary score is created as follows:

- a) Each subscale is multiplied by a constant obtained from table 2 of the US Valuation of EQ-5D-%L Health States Using an International Protocol (Simon et al., 2019)
- b) After subscales have been multiplied by the constant, the index is derived as follows: 1 – absolute value (sum of subscales multiplied by the constant in step a. Lower summary score represents better quality of life. If any items of those 5 items is missing, the summary score is missing.

The EQ VAS score is a separate question on the EQ-5D-5L that represents health status at the time the questionnaire was filled out (0 indicating worst health one could imagine through 100 indicating best health one can imagine).

Section 6.5 of this document describes the analysis for these measures.

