#### 6.1.2 Analysis visits

Information displayed “by visit” will utilize analysis visits based on windows as opposed to the visits at which the information was collected, except baseline information. Baseline can be referred to the date of screening or Day 1 Randomization when a patient is randomized (see Section 1.1 of the study protocol). Analysis day for purposes of the visit windows are derived as follows (the reference date is the randomization date and is considered to be day 1):

- If date of information is missing, analysis day cannot be calculated
- If date of information < reference date, analysis day = analysis date – reference date
- If date of information  $\geq$  reference date, analysis day = (analysis date – reference date) + 1

The visit windows will be as follows for EQ5D and Duke Anticoagulation Satisfaction Scale obtained at month 1, 6, 12, and 24.

Analysis Visit	Analysis Visit Window	Analysis Visit Target Day
Month 1	$1 < \text{analysis day} \leq 45$	30
Month 6	$45 < \text{analysis day} \leq 270$	180
Month 12	$270 < \text{analysis day} \leq 540$	360
Month 24	$540 < \text{analysis day} \leq 900$	720

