#### 6.1.3 End of study

As described in the study protocol (Section 5.8), the original plan for the end of study was defined as that time when the last patient has been followed for 2 years (that patient's 24 month visit). However,

the study has been stopped by the DSMB due to safety concerns, thus the end of study has been modified as 30 days after the last dose of study drug or the end of study date.

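### The 10% missing-data switch for EQ-5D-5L and DASS counts questionnaire visits that had not fallen due when the trial stopped, and so could cost the planned treatment comparison

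*Combined protocol and SAP*

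**What the plan says.** SAP v1.4 section 6.5 sets out a repeated-measures mixed model, fitted by REML to all available data without imputation. It gives apixaban-minus-warfarin differences with 95% confidence intervals at each follow-up time and averaged over time. A condition follows: "if the total missing value is greater than 10%, then descriptive statistics will be presented for the non-missing values by visits and overall".

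This quantity is a ratio. The numerator is "Number of participants missing measure of interest across visits". The denominator is "Number of participants expected to have the measure of interest across visits", spelled out as the number of patients in the population times five visits. The text adds: "Denominator will not take into account when patients died, were lost to follow-up, or withdrew consent".

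The five visits come from SAP v1.4 section 3.4: "The survey is collected at Baseline, Month 1, Month 6, Month 12, and Month 24". Section 3.5 gives the same schedule for DASS. Section 6.1.2 assigns forms to analysis windows: Month 1 is days 2 to 45, Month 6 days 46 to 270, Month 12 days 271 to 540, and Month 24 days 541 to 900.

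Section 6.1.3 states that "the study has been stopped by the DSMB due to safety concerns" and changes the end-of-study definition accordingly.

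**The concern.** The rule treats all five visits as expected from every patient, while the same SAP records that follow-up was cut short. A patient enrolled too late to reach the Month 24 window before the stop still adds a Month 24 slot to the denominator, and the natural reading counts that slot as missing. A threshold meant to detect poor data collection can then be crossed because of the calendar.

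At stake are the two exploratory objectives in SAP v1.4 section 1.1.4, each of which is to compare the arms. The protocol's rationale rests partly on relief from warfarin testing and dietary limits, and DASS asks about such burdens. If the switch operates, the baseline-adjusted differences and their intervals appear to give way to summaries of non-missing values. Those summaries do not handle administrative missingness any better than the model does.

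**Working it through.** **Inputs from the documents.** Five visits; threshold above 10%; windows and target days (30, 180, 360, 720) from SAP v1.4 section 6.1.2; about 1000 patients, hence 1000 × 5 = 5000 slots; 5% loss over two years, stated as a loss hazard of 0.026 (section 6.1.8). The documents state no figure for missing questionnaires. The loss hazard reproduces: −ln(0.95)/2 = 0.0256.

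**Threshold.** Each visit is 1/5 = 20% of the denominator. With every other form complete, total missing = m24/5, where m24 is the share without a Month 24 form. This exceeds 10% only when m24 is above 50%, that is, more than 500 of 5000 slots. Exactly 50% gives exactly 10% and does not trigger the rule.

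**Loss alone.** The planned 5% two-year loss, spread over the five visits by target day, gives about (0.049 + 0.025 + 0.013 + 0.002 + 0)/5 = 1.8%. Planned loss on its own does not reach the threshold.

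**Early stop.** Accrual and stop dates are not given, so these are scenarios. Assume uniform accrual over A days and a last possible form T days after first enrolment. The share not reaching a visit at day d is max(0, (A − (T − d))/A), capped at 1. Total missing is the sum over visits divided by 5. I cap T at 1016 days, from 15 January 2020 (SAP v1.0 file name) to 27 October 2022 (v1.3 file name). That cap assumes enrolment did not precede SAP v1.0, as protocol section 8.4 plans, and that the stop came no later than v1.3, which modified the end of study.

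Two readings bracket each case. *Target day* requires the patient to reach days 30/180/360/720. *Window edge* lets a form on the first day of each window fill the slot (1/45/270/540 days after randomization), which is the most lenient reading.

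Worked example, T = 730, A = 365:
- Target day: Month 24 not reached by (365 − 10)/365 = 97.3%; Month 12 reached by all; total 0.973/5 = 19.5%.
- Window edge: (365 − 190)/365 = 47.9%; total 9.6%.

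| T (days) | A (days) | Stop alone: target day / window edge | Stop plus planned 5% loss |
|---|---|---|---|
| 730 | 365 | 19.5% / 9.6% | 20.3% / 10.4% |
| 850 | 547 | 17.3% / 8.7% | 18.3% / 9.5% |
| 850 | 730 | 24.7% / 15.6% | 25.4% / 16.3% |
| 1016 | 365 | 3.8% / 0% | 5.4% / 1.2% |
| 1016 | 547 | 9.2% / 2.6% | 10.5% / 3.7% |
| 1016 | 730 | 13.9% / 7.0% | 15.1% / 7.9% |
| 1016 | 1016 | 25.4% / 16.9% | 26.3% / 17.5% |

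For the stop alone, five of seven scenarios exceed 10% by target day and two of seven by window edge. With planned loss added, the counts are six and three. At T = 1016 the line is crossed once accrual lasts about 595 days (target day) or 815 days (window edge).

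Closing visits after the stop would lengthen T. In the last row at window edge, 30 extra days (T = 1046, A = 1016) give (510 + 240 + 15)/1016/5 = 15.1%, still above the line.

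**Counting only visits that fell due.** The stop then contributes 0%. With planned loss, missing is 0.8% to 1.7% of due visits across the seven scenarios, so the switch is not reached.

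**The case against.** The strongest objection is the windows. Any form from day 541 fills the Month 24 slot, and the protocol's Schedule of Activities appears to mark the questionnaires at the final study visit. A reader might infer that Month 24 forms were impossible for later enrollees. That is true only of patients with less than about 18 months of follow-up, and under the lenient reading five of the seven stop-only scenarios stay at or below 10%. This stands and limits the claim.

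A reader might also see a unit mismatch, with participants over participant-visits. The two terms are worded in parallel, each a number of participants across visits, so this is loose wording and not an error. If the numerator were meant to hold only visits that fell due, the stop would add nothing, but the text makes no such exclusion.

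A reader might say the model is expressly dropped. The SAP says only that descriptive statistics will be presented. Replacement is implied by the contrasting condition that introduces the sentence, and section 6.1.1 allows ad hoc analyses, so a comparison could still appear, though as unplanned.

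Finally, the rule may be deliberate. The revision history shows that v1.4 modified the missing-value rules after v1.3 had modified the end of study, and section 6.5 openly declines to deduct death, loss or withdrawal. Limiting inference on self-reported scores in an open-label trial stopped for safety is defensible, and REML needs a missing-at-random assumption that death or discontinuation may strain. That is a reason to state the assumption. It does not justify counting unreached visits as missing, and the sentence on deductions does not mention the stop.

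**Conclusion.** The point holds as a possibility. The 10% rule counts visits that had not fallen due at the stop, and these could push the ratio over the threshold by themselves or together with ordinary missingness. The stop-only range is 0% to 25.4% across the scenarios, which rest on assumed uniform accrual and assumed dates. A reader might conclude that the stop will remove the comparison. The documents do not support that, because they give no enrolment dates, stop date or follow-up distribution, and several scenarios stay below 10%. The timing of the revision says nothing about motive.

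The consequence is small. Only the exploratory EQ-5D-5L and DASS objectives are affected, and no primary, secondary or safety conclusion depends on them. This is a cheap improvement.

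**What to change.** Preferred: report the REML treatment differences and confidence intervals in any case. Present the descriptive tables and the missing share by arm and visit in addition, and state that the model estimates assume data missing at random.

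If the 10% switch is kept, define numerator and denominator alike as patient-visits whose analysis window was reached before death, withdrawal or the study stop. Also say explicitly whether exceeding 10% replaces the model or only adds tables.

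Cost: a sentence or two in SAP section 6.5, or a change documented with its rationale in the clinical study report. No new data are needed. The price of the preferred option is reliance on the missing-at-random assumption, which the by-arm missing shares help the reader to judge.

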## 6.6 Interim Analysis

No interim analysis for efficacy or futility is planned. The trial will be completed as planned, unless there is a safety issue that warrants modifying or stopping the trial.

## 6.7 Subgroup Analysis

Subgroup analyses for the primary efficacy outcome will be performed by the following factors at baseline (Day 1 Randomization).

- Age: ≤ 65 years vs. > 65 years
- Race: white vs. non-white
- Sex: female vs. male
- Conduit type: valve alone vs. valve in a conduit
- Baseline apixaban dose: 5 mg BID vs. 2.5 mg BID
- Time from surgery: ≤ 1 year vs. > 1 year
- Valve size (mm): ≤ 21 mm vs. > 21 mm

An additional analysis will be done comparing outcomes by post-randomization TTR in the warfarin arm as <50%, 50-69%, and ≥ 70%. Details of this analysis will be described in a supplementary analysis plan.

There are no guideline or consensus definitions of aortic valve replacement patients who are at high risk of valve thrombosis or valve-related thromboembolism. An additional subgroup analysis will stratify based on the high-risk criteria utilized in the original PROACT trial (Puskas et al., 2018) with high-risk patients defined as having any of the following: atrial fibrillation, left ventricular ejection fraction < 30%, left atrial dimension >50mm, significant vascular disease, and history of neurological events within 1 year.

For each subgroup factor, the linearized event rates of the primary efficacy outcome for both treatment groups and the 95% CI for the difference of linearized event rates will be estimated as Section 6.3.1 above. The ITT population will be used, and statistical testing will be considered exploratory.

## 6.8 Sensitivity Analysis

Three sensitivity analyses are planned for the non-inferiority hypothesis of the primary efficacy outcome – using the NI margin of 1.75%/pt-yr and the OT population, using the NI margin of 1.75%/pt-yr and the AT population, and using a Cox proportional hazard regression model with a hazard ratio of 2 for the NI margin and the ITT population.

For the sensitivity analysis using a Cox proportional hazard regression model, the proportional hazards assumption will be assessed and time from the randomization date to the date of first adjudicated primary composite outcome or censoring will be determined as specified in Section 6.1.6. As mentioned in Section 6.1.6, a sensitivity analysis will be done for all three analysis populations with the more conservative censoring date where all elements of the primary composite outcome were assessed.

The superiority hypothesis for the primary safety outcome will be tested using the ITT and OT populations as sensitivity analyses. Time to the date of first adjudicated major bleeding or censoring will be determined as specified in Section 6.1.6.

## 7 Tables and Figures

### 7.1 List of Tables

#### 7.1.1 Baseline Characteristics

Table 1.1	Demographics
Table 1.2	Cardiac Surgery History
Table 1.3	Warfarin History at Baseline
Table 1.4	Medical History at Baseline
Table 1.4a	Medical History Post Baseline
Table 1.5	Concomitant Medication at Baseline
Table 1.6	Vital Signs and Labs at Baseline

#### 7.1.2 Patient Disposition

Table 2.1	Patient Disposition and Population
-----------	------------------------------------

#### 7.1.3 Study Drug

Table 3.1	Warfarin Adherence and INR
Table 3.2	Apixaban Adherence and Dose
Table 3.3	Aspirin Compliance

#### 7.1.4 Outcome

Table 4.1	Event Rate of Primary Efficacy Outcome
Table 4.1a	Event Rate of Primary Efficacy Outcome by Adjudicated Status
Table 4.2	Hazard Ratio of Primary Efficacy Outcome
Table 4.3	Event Rate of Primary Safety Outcome
Table 4.4	KM Rate of Primary Safety Outcome by Analysis Population
Table 4.5	Death
Table 4.6	Valve Dysfunction
Table 4.7	Non-Thromboembolic Events

Table 4.8	Bleed by Bleeding Classification
Table 4.9	Site of Bleeding
Table 4.10	Hospitalization
Table 4.11	Subgroup Analysis of Primary Outcomes

### 7.1.5 Quality of Life and Satisfaction with Anticoagulation

Table 5.1	EQ-5D-5L Index Score Change Over Time by Treatment
Table 5.2	Duke Anticoagulation Satisfaction Scale Total Score Change Over Time by Treatment

## 7.2 List of Figures

Figure 1	Patient Flow
Figure 2	Kaplan-Meier Curves for Primary Efficacy Outcome
Figure 3	Kaplan-Meier Curves for Primary Safety Outcome
Figure 4	Forest Plot for Subgroup Analyses
Figure 5	EQ-5D-5L Summary Scores over-time by treatment using side-by-side Box-Plots
Figure 6	DASS Summary Scores over-time by treatment using side-by-side Box-Plots

